10.2.1.2 IVR Study Arm

- After download of Fitbit app, patient will need to log-on to website to register with IVR system
- Website to log-in: **secure.aging.uab.edu**
 - Password: **[name]**

Division of Gerontology, Geriatrics, and Palliative Care Logon Page

[figure not shown]
This page is used to access documents.

Palliative Care Resident Library

Study of Aging

Gout Pro Study

- Once password has been entered on website, please have the following information ready
 - Study ID
 - Patient preferred phone number
 - Preferred Call Time

This page is for data entry. 

Subject ID:
Subject phone number:
Preferred call time (Format military time HH:MM):

- Immediately after entering information into webpage a call will need to be placed to IVR system
 - **[contact]) enter 222 and then the study ID**
- Enter study ID using keypad into IVR
- Record patients name, using their own voice and complete first flare assessment using touch-tone keypad on smart phone: **IVR [contact]**
- Make sure the coordinator writes down the preferred call time for IVR system and preferred phone number for future calls
- Remind participant of IVR call schedule.
 - Will be conducted weekly throughout the study period
 - Participant will designate a time for phone calls to be made
 - Confirm preferred phone number for IVR calls

- Provide participant with reminder card and trouble-shooting pamphlet
 - Card will have study ID and phone number
 - Remind participant that study ID will be entered into IVR to confirm participation
- At the end of the visit, the coordinator will send enrollment form, consent form, W9, and preferred phone number, and call time to UAB ([contact])

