10.1 Overview

At enrollment a questionnaire will be completed by all participants to capture demographics, gout-specific disease history, type of phone used. If participants meet I/E criteria (see Tab 1.1) they will be offered consent for the study (see Tab 2.2).

RheumPPO is a mobile smartphone application developed by UAB to capture Patient Reported Outcomes and data from electronic health trackers like Fitbit. Installation of RheumPRO is required for all participants to ensure that passive data can be collected from study provided Fitbit (<https://www.fitbit.com/>) that will be provided to all enrolled participants (see below). We are exploring the use of passively collected FitBit data to see if more timely prompts to patients regarding gout flares can be determined. Passively collected data will include: steps, distances, heart rate, floors, minutes at various activity levels, and sleep parameters.

Phase 1:

After consenting to participate in the study participants will be randomized to start with the IVR or RheumPRO intervention (Phase 1) groups. Frequency and questionnaire prompts for each system will be matched.

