The IVR system includes tailored scripting of Gout Flare and Patient Reported Outcome questions (with skip logic), recorded by a member of the research team. The system will automatically dial participants at a schedule time (eg. Monday 4 PM) and if no answer will attempt 2 more times at the same time over the following 2 days (eg. Tuesday 4 PM, Wednesday 4 PM). Participants will self-navigate through the questions using their telephone keypad. Participants can also call into the system to complete surveys if they experience a flare on a day they are not scheduled to receive a call. The IVR system will be programmed to call the patient weekly for 12 weeks to complete a weekly Gout Flare Survey. Consistent with the published gout flare self-report definition, gout flare ascertainment questions will include whether the recent flare is similar to past flares, the number of swollen joints and the number of warm joints. Pain at rest during the attack will be assessed on a 0-9 scale. Together, these questions attain 90% accuracy with physician-diagnosed gout. Further questions will include peak pain, timing of attack and duration of attack if completed. We will capture patient reported outcome measures (e.g. pain, fatigue, sleep) using instruments from the NIH PROMIS assessment center (<https://www.assessmentcenter.net/>). In addition IVR questionnaires at months 1, 3, and 6 will assess IVR ease of use, burden of use, willingness to continue use and disruption to daily activities. At enrollment the study coordinator will explain how the IVR works, planned survey schedule, and that participant -initiated calls to IVR are allowed.

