Participants randomized in Phase 1 to the RheumPRO application will complete the exact same Gout Flare Survey questions as the participants randomized to the IVR group, but will complete them using the RheumPRO application that will be downloaded on their smartphone. The RheumPRO application will be programmed to notify participants weekly for 26 12 weeks via a scheduled (eg. Monday 4 PM) “pop-up” to complete Gout Flare and Patient Reported Outcomes Surveys. Participants self-navigate through the survey questions using their smartphone. If participants do not complete the Gout Flare RheumPRO will generate 2 more “pop-ups” at the same time over the following 2 days (eg. Tuesday 4 PM, Wednesday 4 PM). Participants can also open the RheumPRO application on their smartphone and complete surveys or if they experience a flare on a day they are not scheduled to complete a survey. In addition, RheumPRO questionnaires at months 1, 3, and 6 will assess RheumPRO ease of use, burden of use, willingness to continue use and disruption to daily activities. At enrollment the study coordinator will explain how RheumPRO works, planned survey schedule, and that participant -initiated surveys in RheumPRO are allowed.

Phase 2:

At the conclusion of 12 weeks individuals will “crossover” to the opposite study arm and will continue in the study for an additional 12 weeks using the opposite technology to report their flare frequency/intensity (i.e., those randomized to IVR for the first phase will use the RheumPRO app in the second phase and vice-versa) completing the exact same Gout Flare and Patient Reported Outcome questions as were completed in Phase 1. Activities to be completed at each study visit are detailed below.

Figure 1. Study Workflow

[figure not shown]

Table 1. Study Visits and Evaluation

[figure not shown]
	1	2	3	4	5	6	7	8	9	10	11	12	13	14	15	16	17	18	19	20	21	22	23	24	
Informed Consent	X																								
Paper Screening	X																								
Paper Enrollment	X																								
IVR/RheumPRO Initial Flare Assessment	X																								
Patient- Weekly Flare Assessment*		X	X	X	X	X	X	X	X	X	X	X	X	X	X	X	X	X	X	X	X	X	X	X	X
2 week adherence call		X																							
1-month follow-up Assessment and phone check-in				X																					
3-month follow-up Assessment												X													
Crossover Study Visit†													X												
1-month follow-up Assessment and phone check-in																		X							

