 7. Popup window will be displayed when app is opened requesting “DevRheumPRO would like to send you notifications, press “OK”

8. If new to RheumPRO click on register
9. The app will prompt you to reference the physical consent document for the study. It will ask you to press next
10. The next screen will ask the participant to answer whether they have signed the physical consent document
11. If they have, press agree and a new screen will ask them to sign with their finger and type in their name and submit

12. The next several screens require the participant to create an account. They will need to provide (the questions are spread out over 4 separate screens):

- Email address
- Password
- First/Last Name
- Relationship to Arthritis: Patient, Caregiver, etc.
- Sex
- Race
- Date of Birth
- Country
- Zip Code

Step 2 of 4

First Name:

Last Name:

Relationship to Arthritis:

Sex:
 Male
 Female

Race:

Hispanic:

Date of Birth:

Twitter Handle: Optional

- Twitter Handle is not a required field**

Step 3 of 4

Country:
 United States of America

Postal Code:
 00000

A valid zipcode is required

Filling in the optional fields below may help us personalize your news, research opportunities and link your account to other services more efficiently in the future.

State: Optional
 Select State

City: Optional
 City

Address Line 1: Optional
 Street/PO Box/etc

Address Line 2: Optional
 Apt/Suite/etc

Previous Next

- Postal Code/Zip is required; address is not **

Step 4 of 4

Select diseases that you have been diagnosed with:

Ankylosing Spondylitis
 Dermatomyositis
 Fibromyalgia
 Gout
 Inflammatory Bowel Disease
 Juvenile Idiopathic Arthritis
 Lupus
 Osteoarthritis (degenerative arthritis)
 Osteoporosis/Osteopenia/low bone mineral density
 Polymyositis
 Psoriasis
 Psoriatic Arthritis
 Rheumatoid Arthritis
 Scleroderma (systemic sclerosis)

Select Insurance

[figure not shown]
Medicare
 Medicare Advantage
 Medicaid
 Tri-care / Military
 Commercial/Private insurance
 Other type of insurance
 No insurance

I Have a Rheumatologist

[figure not shown]
Previous Submit

- There is no need to click on the “I have a rheumatologist” button. It is not necessary for the app registration**

13. Upon completion of registration the app homepage will be displayed. In order to give permission for RheumPRO to access the Fitbit data, click on “Health Devices”

14. An icon with “Fitbit” and a “+” will be displayed.
15. Click on the “+” to add the participants Fitbit.

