10.2.2 Visits 2-12

- Visits 2-12 will be completed by participant using IVR or RheumPRO application
- Participants will receive notification the day of, 24 hours, and 48 hours later
 - IVR will call participant at designated time to complete
 - RheumPRO will send push notifications participants to complete survey

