10.2.5.1 RheumPRO Participant

- In the event that the participant has a gout flare in-between the scheduled weekly surveys the participant can open the RheumPRO app and complete a survey
 - Describe the process of opening the app and finding the interval gout flare assessment survey icon to the participant
 - Stress to them the importance of completing this form ONLY when they feel they are having a gout flare

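### IVR set-up has participants choose the prompt time while RheumPRO set-up is silent on it, and the ad hoc instruction is worded more strictly for RheumPRO; both differences go with mode in each phase.

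*Combined protocol and SAP*

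**What the plan says.** Section 10.1 (Overview) sets the intent: "Frequency and questionnaire prompts for each system will be matched". It then describes the two modes in nearly parallel terms. For IVR, "The system will automatically dial participants at a schedule time (eg. Monday 4 PM"; for the app, "The RheumPRO application will be programmed to notify participants weekly for 26 12 weeks via a scheduled (eg. Monday 4 PM". Both modes get two repeat prompts at the same hour on the next two days, use the same flare questions, and allow participant-initiated reports.

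The set-up instructions are less parallel. Section 10.2.1.2 (IVR, Visit 1) tells the coordinator that "Participant will designate a time for phone calls to be made", and the registration page has the field "Preferred call time (Format military time HH:MM". Section 10.2.3.2 repeats both for participants who cross over to IVR. For the app, Sections 10.2.1.1 and 10.2.3.1 go screen by screen: "The next several screens require the participant to create an account", followed by a list of fields that does not include a notification time. In Section 10.2.2 the IVR call comes at the designated time, while for the app the text is only "RheumPRO will send push notifications participants to complete survey".

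On unscheduled reports, Section 10.2.5.1 instructs staff about RheumPRO users: "Stress to them the importance of completing this form ONLY when they feel they are having a gout flare". Section 10.2.5.2 lets IVR users call in to report a flare and carries no equivalent emphasis.

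**The concern.** The study compares two ways of collecting the same information, so anything else that differs systematically between the modes is mixed into the comparison. A coordinator who follows the text exactly would ask an IVR participant for a convenient time and would have no prompt to ask a RheumPRO participant. The same coordinator would give RheumPRO users a firmer warning about unscheduled reports.

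What is at stake is attribution. Section 10.1 collects ease of use, burden, willingness to continue and disruption for each mode, and Section 13 tests RheumPRO against IVR with paired methods. Whether people chose the time at which they are interrupted bears plausibly on burden and disruption, and perhaps on weekly completion. A stricter instruction bears plausibly on the number of ad hoc reports. A difference on any of these could come from the set-up text and not from the technology, and this cannot be untangled once the data are in.

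**Working it through.** The plan states no figure on this point, so the check is a side-by-side reading followed by a short argument about the design.

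**Prompt time**
- Overview (10.1): both modes are scheduled weekly with the same example slot. Neither description says who chooses the slot.
- Visit 1: IVR has a participant-designated time, a form field for it, and an instruction to the coordinator to write it down (10.2.1.2). RheumPRO has installation, account and tracker-linking steps, with no step or listed field for a time (10.2.1.1).
- Crossover: the same contrast (10.2.3.2 against 10.2.3.1). Nothing says that a time already given for IVR is carried into the app.
- Weekly visits: 10.2.2 refers to a designated time for IVR only. 10.2.4 refers to designated intervals for IVR and to push notifications for RheumPRO.
- The IVR field holds hours and minutes only, and no weekday is recorded.

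**Ad hoc reports**
- Overview (10.1): in both modes participants may report a flare that falls on an unscheduled day.
- Section 10.2.5: one shared rule for both modes.
- Section 10.2.5.1 (RheumPRO): adds an explicit restriction for staff to stress.
- Section 10.2.5.2 (IVR): states the purpose as reporting a flare, without that restriction.

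**Why crossing over does not help**

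Let τ be the effect of the technology (IVR minus RheumPRO), δ the effect of the set-up differences that accompany IVR, and π1 and π2 the period effects. Ignoring carryover, the expected within-person difference (IVR minus RheumPRO) is:
- IVR first: τ + δ + (π1 − π2)
- RheumPRO first: τ + δ − (π1 − π2)

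The average over the two sequences is τ + δ. The person effect cancels within each pair, and the period effect cancels when the sequences are balanced. δ does not cancel, because it has the same sign in both sequences. The paired t test, McNemar's test and the signed rank test in Section 13 all work on these within-person contrasts, so none of them separates τ from δ. Sections 13 and 14 contain no other step that would.

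**Size**

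δ cannot be estimated. The documents give no response rate by mode, no within-person standard deviation and no sample-size calculation. The 45 in Section 8 is the number of participants to be supplied with trackers, not a count of completed pairs. On direction, one can only assume: if choosing a time helps completion and a firmer warning discourages unscheduled reports, both would favour IVR on the number of reports.

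**The case against.** The strongest reply has four parts.

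First, a reader might infer that the set-up text contradicts the matching promised in Section 10.1. It does not. That sentence covers frequency and questionnaire prompts, not who picks the clock time, and the rest of 10.1 delivers what it promises. This part of the reply stands: there is a gap in the matching, not a contradiction of it.

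Second, a reader might infer that RheumPRO pop-up times are fixed by the study. No sentence says so. The app steps concern installation and accounts, the screen images are missing, and the example slot in 10.1 is introduced in the same way for both modes. This also stands: the documents support only the statement that the RheumPRO time is unspecified.

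Third, IVR ad hoc calls are also described as being for flares, so the difference is in emphasis and not in the rule. Both modes then ask the same flare-definition questions, so a stray entry need not count as a flare. This stands as well, though an instruction that staff are told to stress in one mode only can still change how often people report.

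Fourth, a live call has to be answered when it arrives, so arranging its time may be part of delivering IVR, and a feasibility pilot may compare the systems as delivered. That is a legitimate aim, but the protocol does not state it, and its own matching sentence points towards making the modes alike. Section 13 also does not name weekly completion or ad hoc counts as paired-test endpoints. The measures it names are preference and satisfaction surveys, so the exposure for those counts is less certain than for burden and disruption.

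**Conclusion.** The point holds as a minor, avoidable asymmetry. Followed literally, the set-up text gives IVR participants a say in the prompt time and leaves the RheumPRO time undefined, and it gives RheumPRO users a firmer instruction on ad hoc reports. Both differences go with the mode in each phase, so they could affect mode comparisons of burden, disruption, completion and ad hoc reports, and the planned paired analysis cannot separate them from the technology.

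The conclusion rests on two assumptions: that coordinators follow the steps as written, and that nothing outside these documents already sets the RheumPRO time by participant choice. The size is unknown. A reader might be tempted to put a false-positive rate on it, but that would need an assumed shift, an assumed standard deviation and a number of complete pairs, none of which the documents supply, so no figure is given. Nor do the documents show that the mode comparison is invalid; they show that it is less clean than it could be at almost no cost.

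**What to change.** - At Visit 1, record one prompt slot for every participant, whichever mode comes first, using the same field or fields in both modes. The IVR form now holds only a time of day, so either keep time only in both modes or add the weekday to both. Adding a weekday for RheumPRO alone would create a new mismatch.
- Program IVR and RheumPRO to that slot, and carry it unchanged through the crossover at Visit 13. Sections 10.2.1.1, 10.2.1.2, 10.2.3.1 and 10.2.3.2 should say so in the same words. If RheumPRO times are already chosen by the participant, the protocol should state this.
- Use identical ad hoc reporting wording in Sections 10.2.5.1 and 10.2.5.2.
- If the sponsor prefers to keep the procedures as they are, state that the comparison is of each mode together with its set-up.

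The cost is a minor form change, some notification programming and a few lines of text. It needs no extra visits or staff.

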10.2.2 Visits 2-12

- Visits 2-12 will be completed by participant using IVR or RheumPRO application
- Participants will receive notification the day of, 24 hours, and 48 hours later
 - IVR will call participant at designated time to complete
 - RheumPRO will send push notifications participants to complete survey

10.2.3 Visit 13 (Crossover Visit)

- Coordinator will call/schedule crossover visit 7 days in advance and remind participant to bring smart phone and Fitbit
- Patients will return to clinic to complete crossover visit to switch to the opposite arm of the study

[figure not shown]
10.2.3.1 *New RheumPRO participant*

- RheumPRO app installation
 - Coordinator will type in web address to access RheumPRO application
 1. Web Address <https://dev-rheumpro.hs.uab.edu/goutpro/>
 - Once participant accesses the link via their smart phone, identify either iPhone or Android
 - There is a possibility of connectivity issues with the RheumPRO app
 1. For Android Users it will prompt the download of the APK which they can then install.
 2. If you are unable to connect try another Wi-Fi network
 3. If unsuccessful try downloading the app or reloading app page using cellular data
 - After password is entered, a page description of the app, click on “install application will be seen, and a pop-up window will appear to confirm installation

- Once the install application button has been selected, there are a series of direction on the screen prompting the participant to be sure the installation has proceeded. Helpful pointers are listed below:
 1. “in progress”:
 - Installation will be performed in the background (since iOS7): check the icons on device’s home screen
 2. “or not”
 - If the iOS popup “Would you like to install...” did not appear, check that participant doesn’t already have the same app installed from the AppStore
 - If an app with the same bundle identifier is already installed on the device from the AppStore, nothing will happen
 - Delete the app installed from the AppStore to be able to install this one
 3. “Nothing seems to happen”
 - After tapping the “install” button in the popup, if nothing seems to happen and participant is still on the same page, check device home screen: the installation should be in progress: should see the icon of the app somewhere and a progress bar
 4. “Unable to download app popup”
 - First check internet connection, and be sure that device is not behind a firewall that may prevent downloading .ipa files
 - Most common installation issues are:
 - Expired provisioning profile
 - Incompatible device (check iOS version, device family, and required device capabilities)
 5. If a popup with “untrusted enterprise developer” is displayed.
 - Direct participant to settings -> General-> Device Management-> Click on appropriate Enterprise App (University of Alabama at Birmingham and click trust
 - Add layout for android
 6. Now go back to homepage and click on app

- Popup window will be displayed when app is opened requesting “DevRheumPRO would like to send you notifications, press “OK”

7. If new to RheumPRO click on register
8. The app will prompt you to reference the physical consent document for the study. It will ask you to press next
9. The next screen will ask the participant to answer whether they have signed the physical consent document
10. If they have, press agree and a new screen will ask them to sign with their finger and type in their name and submit
11. The next several screens require the participant to create an account. They will need to provide (the questions are spread out over 4 separate screens):
 - Email address
 - Password
 - First/Last Name
 - Relationship to Arthritis
 - Sex
 - Race
 - Date of Birth
 - Country
 - Zip Code

Step 2 of 4

First Name:
First Name

Last Name:
Last Name

Relationship to Arthritis:
Select Relationship to Arthritis

Sex:
 Male
 Female

Race:
Select Race

Hispanic:
Select Hispanic

Date of Birth:
[Dropdown]

Twitter Handle: **Optional**
Twitter Username

Previous Next

- Twitter Handle is not a required field**

Step 3 of 4

Country:
United States of America

Postal Code:
00000

A valid zipcode is required

Filling in the optional fields below may help us personalize your news, research opportunities and link your account to other services more efficiently in the future.

State: **Optional**
Select State

City: **Optional**
City

Address Line 1: **Optional**
Street/PO Box/etc

Address Line 2: **Optional**
Apt/Suite/etc

Previous Next

- Postal Code/Zip is required; address is not **

Step 4 of 4

Select diseases that you have been diagnosed with:

Ankylosing Spondylitis

Dermatomyositis

Fibromyalgia

Gout

Inflammatory Bowel Disease

Juvenile Idiopathic Arthritis

Lupus

Osteoarthritis (degenerative arthritis)

Osteoporosis/Osteopenia/low bone mineral density

Polymyositis

Psoriasis

Psoriatic Arthritis

Rheumatoid Arthritis

Scleroderma (systemic sclerosis)

Select Insurance

Medicare

Medicare Advantage

Medicaid

Tri-care / Military

[figure not shown]
Commercial/Private insurance

Other type of insurance

No insurance

- There is no need to click on the “I have a rheumatologist” button. It is not necessary for the app registration**

12. Upon completion of registration the app homepage will be displayed. In order to give permission for RheumPRO to access the Fitbit data, click on “Health Devices”

13. An icon with “Fitbit” and a “+” will be displayed.
14. Click on the “+” to add the participants Fitbit.
15. A log-in page will be displayed and the participant will need to add their Fitbit login credentials
16. **A new page will be displayed asking for permission to access the Fitbit data. We want to have access to all 4 fields. Press Allow to complete authorization**

17. The next page will be a confirmation screen, and hit done in the bottom left corner to return to the home page.

18. The initial flare assessment should be available to complete. Please make sure the participant completes this survey before leaving

- Provide participant with reminder card and trouble-shooting pamphlet
 - Don't forget to fill in study ID, RheumPRO account information, and Fitbit account information.

